4.1.2. Exclusion Criteria

A participant will not be eligible for this study if he/she meets any of the following criteria:

1. CAH not due to 21-OHD.
2. History of allergy or hypersensitivity to tildacerfont or other CRF₁ receptor antagonist.
3. History of bilateral adrenalectomy or hypopituitarism.
4. Current treatment with dexamethasone. Participants may be transitioned off dexamethasone prior to Screening at the Investigator's discretion.
5. A clinically significant unstable medical condition, medically significant illness, or chronic disease (other than CAH) within 30 days, including but not limited to:
 - a. Malignancy or < 3 years of remission, except successfully treated localized skin cancer
 - b. Estimated glomerular filtration rate (eGFR) of $< 45 \text{ mL/min}/1.73 \text{ m}^2$ (per the creatinine-based Schwartz equation)

- c. Current or history of liver disease (with the exception of Gilbert's syndrome). Resolved/cured viral hepatitis may be allowed with MM approval
- d. History of alcohol or substance abuse within the last year, or otherwise that would likely prevent the participant from reliably or safely participating in the study, per Investigator judgement
- e. HIV at Screening
- f. Any other condition that would impact participant safety or confound interpretation of study results, in the opinion of the Investigator or MM.

6. Psychiatric conditions, including but not limited to major depression, bipolar disorder, schizophrenia, or schizoaffective disorders that are not effectively controlled on medication and may have an adverse impact on study compliance. Exclusionary symptoms include hallucinations, delusions, and psychosis. Baseline values for depression and anxiety questionnaires are not exclusionary but may inform exclusion of a participant based on Exclusion Criterion 5.

7. Clinically significant abnormal clinical laboratory or ECG results during Screening. Abnormal results requiring review and discussion with the MM to discern eligibility include, but are not limited to:

- a. Any clinically meaningful abnormal ECG results, including QTcF >450 ms (males) or >460 ms (females)
- b. Alanine aminotransferase (ALT) >2x upper limit of normal (ULN)
- c. Total bilirubin >1.5x ULN (except if due to Gilbert's syndrome).

8. Females who are pregnant or nursing.

9. Use of any other investigational drug (other than tildacerfont) or device within 30 days or 5 half-lives (whichever is longer) prior to Screening through the end of the study (EOS). Prior exposure to tildacerfont is allowed, but tildacerfont should be discontinued for at least 2 weeks prior to randomization. The screening window may serve as the washout period.

10. Use of the following drugs from 30 days or 5 half-lives (whichever is longer) before Screening through the EOS (see [Appendix 3](#)):

- a. Rosiglitazone, testosterone, growth hormone, or any other medication or supplement that could impact participant safety or confound interpretation of study results
- b. Moderate to strong inhibitors and/or inducers of CYP3A4
- c. Sensitive substrates or narrow-therapeutic-range substrates of CYP3A4 (except hormonal contraception containing \leq 20 mcg ethinyl estradiol)
- d. Sensitive substrates or narrow-therapeutic-range substrates of BCRP (except those that can be administered QD in the morning, separated by approximately 10 hours from evening administration of study drug).

11. Donation or receipt of blood from 90 days before Screening through the EOS; donation or receipt of platelets, white blood cells, or plasma from 30 days before Screening through the EOS.

12. Any known or anticipated swallowing difficulty or dysphagia during Screening or the duration of the study.

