Figure 1. Overall Study Design for Cohorts 1, 1a, 2, and 3

Cohort	Age (years)	Corresponding Adult Dose
1	11 to 17	50 mg QD
1a*	11 to 17	To be determined based on DMC recommendation
2	11 to 17	200 mg QD
3	2 to 10	50 mg QD, 100 mg QD, OR 200 mg QD

*Cohort 1a is an optional interim dose cohort that may be enrolled only if needed per DMC recommendation and Sponsor decision, in the event of a safety concern in sentinel participants in Cohort 1.

[figure not shown]
[figure not shown]

Figure 2. Overall Study Design for Cohorts 4, 5, 6, 8, 7, and 9

Note: Any participant enrolled under protocol amendment 3 may be re-consented to protocol amendment 4 and receive the 12-week treatment course; however, because they will have already contributed PK data, they will not be required to have blood draws for tildacerfont concentration on Days 1 and 14 between 0.5 to- 1.5 hours and between 3 to 5 hours post dosing. Additionally, any participant enrolled under amendment 4 (or any other tildacerfont study) may be re-consented and enrolled under protocol amendment 5.

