3.1.2. Study Visits

Each participant will undergo a Screening Period of up to approximately 14 days, a 12-week (Cohorts 1 to 3) or 4-week Treatment Period (Cohorts 4 to 9), and a 30-day Safety Follow-up Period. The Screening Period may be extended as approved by the Sponsor and/or contract research organization (CRO) designee. The Schedule of Activities for the study is provided in [Appendix 1](#) and [Appendix 3](#) for Cohorts 1 to 3 and Cohorts 4 to 9, respectively. The Schedule of Activities for the extension is in [Appendix 2](#) and [Appendix 4](#), respectively.

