6.1.4. QT Stopping Criteria

Study drug will be discontinued for a participant if either of the following criteria is met:

- QTcF >500 msec OR uncorrected QT >600 msec
- Change from Screening in QTcF of >60 msec

One repeat ECG should be performed to confirm the accuracy and persistence of an initial result that fulfills the QT stopping criteria.

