Cohorts 4, 5, 6, and 7 PD markers and tildacerfont concentration (single sample) ⁸ (also 8 and 9 if indicated)				X	X	X ⁶
A4-based GC dose adjustment ¹⁰				X		
Weight-based tildacerfont dose adjustment	X					
Urinalysis ¹¹	X		X		X	X ⁶

CONFIDENTIAL

Page 81 of 87

SPR001-205

Spruce Biosciences, Inc.

CLINICAL STUDY PROTOCOL

Version 5.0

	Screening ¹	Treatment Period			Early Termination	Safety Follow-up ²
		Day 1	Week 2	Week 4 (EOT)		
VISIT NUMBER	1	2	3	4		5
STUDY DAY	≤14 days before V2	1	14	28		Last dose +30 days
Visit windows			+3 days	±3 days		± 7 days
Vital signs ¹² , body weight	X	X	X	X	X	X ⁶
Physical exam ¹³	X	X	X	X	X	X ⁶
12-lead ECG	X		X ¹⁴		X	X ⁶
Bone age and predicted adult height ¹⁵	X					
C-SSRS ¹⁶	X		X	X	X	X ⁶
PROMIS ¹⁷	X		X	X	X	X ⁶
SWYC ¹⁸	X		X	X	X	X ⁶
Dispense study drug ¹⁹		X				
Study drug accountability			X	X	X	
Clinic drug administration ²⁰		X	X			
Review any AEs		X	X	X	X	X

Abbreviations: 11KT=11-ketotestosterone; A4=androstenedione; ACTH=adrenocorticotropin hormone; AEs=adverse events; ALT=alanine aminotransferase; ALP=alkaline phosphatase; AST=aspartate aminotransferase; CRO=contract research organization; C-SSRS=Columbia–Suicide Severity Rating Scale; ECG=electrocardiogram; eGFR=estimated glomerular filtration rate; EOT=end of treatment; ET=early termination; FOCP=female of childbearing potential; GC=glucocorticoid; GGT=gamma-glutamyl transferase; HIV=human immunodeficiency virus; EP=open-label extension; PD=pharmacodynamics; PK=pharmacokinetics; PROMIS=Patient Reported Outcomes Measurement Information System; 17-OHP=17-hydroxyprogesterone; SWYC=Survey of Well-being of Young Children; T=testosterone.

¹ The Screening Period may be extended as approved by the Sponsor or CRO designee.

² For participants continuing in the EP period, the Safety Follow-up Visit will be 30 days after their last dose in the EP Period.

³ A pregnancy test will be performed at every visit for FOCP. The Screening Visit will include a serum pregnancy test. All subsequent visits will include urine pregnancy tests. Any positive urine pregnancy test must be followed up by a serum pregnancy test for confirmation.

⁴ Labs will be drawn at approximately 8 AM (±1 h) before any morning dose of GC medication.

⁵ Laboratory assessments include: A4, coagulation panel (Screening only), hematology, chemistry (including liver function tests AST, ALT, ALP, GGT, total and direct bilirubin, and total bile acids), thyroid panel. Fasting is not required.

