### 9.2.2 *Re-Enrolled, Different Cohort*

Re-enrolled subjects will have more than one set of cohort data. Therefore, the summary results by cohort will be summarizing these subjects by unique enrollment experience (per cohort) rather than per subject for summaries of disposition, protocol deviations and study drug exposure. Subjects who re-enrolled into two or more different cohorts will have multiple baseline values for safety and efficacy summaries – a set of baseline values for their first cohort experience, and a set of baseline values for each subsequent cohort experience.

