#### 9.4.9 Baseline Values

Baseline values are defined as the last non-missing assessment that is on or prior to the date of the first dose of study drug in each cohort. If the date and time of an assessment are collected, then the date and time are compared against the first dose date and time; otherwise, if only the date of an assessment is collected, the baseline assessment will be the last non-missing assessment collected on or prior to the date of the first dose of study drug. A4, 17-OHP, and ACTH baseline values are defined as the mean of measurements collected between Screening (Visit 1) and Day 1 (Visit 2).

Subjects who re-enrolled into the same cohort, the last-non-missing assessment prior to the second enrollment's first dose of study drug will be used as baseline.

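### For participants who re-enter from another cohort or tildacerfont study, the SAP's averaged A4 baseline can include a Screening value drawn on drug

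*Protocol*

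**What the plan says.** Protocol 4.1.2, exclusion 9, states: "Prior exposure to tildacerfont is allowed, but tildacerfont should be discontinued for at least 2 weeks prior to randomization". It then adds: "The screening window may serve as the washout period". Protocol 3.1.2 sets the length: "Each participant will undergo a Screening Period of up to approximately 14 days". Sections 3.1.2 and 3.1.2.1 allow it to be extended with approval.

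Re-entry is planned for. The note under Figure 2 in Protocol 3.1 says that "any participant enrolled under amendment 4 (or any other tildacerfont study) may be re-consented and enrolled under protocol amendment 5". SAP 9.2.2 covers participants who move to a different cohort and gives them "a set of baseline values for each subsequent cohort experience".

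A4 is measured at Screening in Cohorts 4-9. Protocol Appendix 3, footnote 5, reads: "Laboratory assessments include: A4, coagulation panel (Screening only), hematology". SAP 9.4.9 departs from its general last-value rule for three hormones: "A4, 17-OHP, and ACTH baseline values are defined as the mean of measurements collected between Screening (Visit 1) and Day 1 (Visit 2"). For re-enrolment into the same cohort, the same section goes back to the last value before the new first dose. It gives no such rule for a different cohort or for entry from another study.

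**The concern.** The baseline of a Week 4 A4 comparison should describe the participant off drug. A participant who uses the screening window as washout contributes one value taken under the drug being tested and one taken after it has been withdrawn. The protocol reports that tildacerfont lowers A4, so the averaged baseline is expected to be too low and the change from it too small.

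This feeds the secondary endpoint of A4 reduction at Week 4 in Cohorts 4-9. It also feeds the exploratory change, percent change, geometric mean ratio and 50% reduction summaries (SAP 13.2.1 and 13.2.3). Cohorts are of about 5, or 10 where two doses are tested, so a few such participants can shape a cohort's result.

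**Working it through.** The plan states no figure on this point, so there is none to reproduce.

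**Timeline.** Screening is at most about 14 days before Day 1, and the drug must stop at least 14 days before dosing restarts. The stated anchor, randomization, does not exist in this study (SAP 5.1), so Day 1 is taken as the anchor. Without an extension, both conditions fit only if the last dose falls at about Visit 1. With an extension, dosing can continue past Visit 1. Either way the Visit 1 sample reflects dosing.

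**Baseline.** Assumptions:
- Off-drug A4 is B, and on-drug A4 is (1 − f)B. The documents describe the reduction in adults only as meaningful, so f is set at 20%, 30% and 50%.
- A4 has fully recovered by Day 1.
- Two values enter the mean: Screening and Day 1 pre-dose.

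Then baseline = [(1 − f)B + B]/2 = (1 − f/2)B. A true Week 4 fall r appears as 1 − (1 − r)/(1 − f/2). It counts as any reduction only if r > f/2, and as a 50% reduction only if r ≥ 0.5 + f/4.

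| f | Baseline / B | A true fall of r = f appears as | True fall needed for any reduction | True fall needed for 50% category |
|---|---|---|---|---|
| 20% | 0.90 | 1 − 0.80/0.90 = 11.1% | more than 10% | 55% |
| 30% | 0.85 | 1 − 0.70/0.85 = 17.6% | more than 15% | 57.5% |
| 50% | 0.75 | 1 − 0.50/0.75 = 33.3% | more than 25% | 62.5% |

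**Cohort level.** If one of five participants is affected at f = 30%, the cohort geometric mean ratio is multiplied by 0.85^(−1/5) = 1.033, so a true 0.70 reads 0.72. If all five are affected it is multiplied by 1/0.85 = 1.176 and reads 0.82.

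**Incomplete recovery.** If A4 has recovered only halfway by Day 1, the averaged baseline is (0.70 + 0.85)/2 = 0.775 at f = 30% and (0.50 + 0.75)/2 = 0.625 at f = 50%. A true fall of f then appears as 9.7% and 20%. With no recovery it appears as 0%. No half-life is given, so recovery by Day 1 cannot be checked.

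**Within-person variation.** A simulation of 400,000 draws assumed a within-person SD of 0.3 or 0.5 on the log scale and a Week 4 value at (1 − f) of off-drug A4. The chance of showing any reduction at f = 30% was:

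| SD | Two off-drug values | One on-drug, one off-drug | Day 1 alone |
|---|---|---|---|
| 0.3 | 0.85 | 0.72 | 0.80 |
| 0.5 | 0.75 | 0.66 | 0.69 |

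At f = 50%, the chance of a 50% reduction fell from 0.52 to 0.24 (SD 0.3) and from 0.54 to 0.35 (SD 0.5).

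**Normalisation.** SAP Table 5 compares the post-baseline value with the upper limit of normal (ULN). Baseline does not enter.

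**The case against.** Much of the other side stands.

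- **Secondary endpoint.** A reader might infer that real responses are generally missed. At the table's own values the apparent falls are 11%, 18% and 33%, and all still count as reductions. Without measurement variation, a responder is lost only when the true fall is below f/2. One lost responder in a cohort of five is 20 percentage points, but the illustrated cases lose none.
- **Eligibility.** A reader might infer that the A4 range in inclusion 4 (1.2 to 4 times ULN) admits the wrong patients. Applied on drug, it corresponds to 1.71 to 5.71 times ULN off drug at f = 30%. However, inclusion 4 names no time point, the Medical Monitor may accept values outside the range, and Protocol 4.3 lets an exclusionary laboratory value be retested before treatment. Criteria are also re-confirmed on Day 1, although nothing says a Day 1 A4 result is available before dosing.
- **QTcF.** Protocol 6.1.4 uses "Change from Screening in QTcF of >60 msec", and a reader might infer that a drug effect is already in the reference. The documents do not show this. Protocol 1.3 reports only mild, possibly treatment-related pre-clinical trends and no cardiovascular concern in human monitoring. Appendix 3 footnote 14 and SAP 5.3.1.5 describe a Day 1 pre-dose ECG, although the schedule table and Visit 2 list omit it. The absolute QT limits do not depend on a reference value.
- **Scope.** The washout clause is permissive, and the re-enrolment note does not name Cohorts 4-9. The opening of SAP 9.2 and Section 9.2.1 are not in the text available here, so a wider exception cannot be fully excluded, though the title of 9.2.1 limits it to the same cohort.
- **Weight.** The primary endpoint is safety, efficacy is descriptive, and the bias runs against the drug.

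None of this removes the baseline problem: the SAP as written averages the two values.

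**Conclusion.** The point holds for the A4 baseline. Following the plan, a participant who uses the screening window as washout and enters Cohorts 4-9 from a different cohort or study gets a baseline that is low by f/2: 10%, 15% or 25% for f of 20%, 30% or 50%. Percent change and the 50% category are understated, and true falls smaller than f/2 are scored as no reduction.

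These sizes rest on an assumed f and on full recovery by Day 1. Incomplete recovery makes the understatement larger. The number affected is unknown. Protocol 1.2.3 reports 30 children already treated in Cohorts 1-3, which suggests the size of one source but not how many will use the option.

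The documents do not support stronger conclusions about normalisation through the baseline, about wrong enrolment, or about a blunted QTcF rule. For eligibility and QTcF, what stands is that the documents do not make clear which values are meant to be off drug.

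**What to change.** **SAP 9.4.9.** Add one sentence before database lock: for any participant who took tildacerfont at Visit 1, within 2 weeks before it, or between Visit 1 and Day 1, the A4, 17-OHP and ACTH baseline is the Day 1 pre-dose value alone. The Appendix 3 Screening panel lists only A4 of the three, so for the other two this is mainly a safeguard. With full recovery the bias becomes zero. With half recovery at f = 30% the baseline improves from 0.775 to 0.85 of the off-drug value.

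**Cost.** The Day 1 pre-dose sample is already scheduled. These few participants get a single-value baseline alongside averaged ones, which is noisier: in the simulation at f = 20% and SD 0.5, the chance of any reduction was 0.61 with the mixed mean and 0.62 with Day 1 alone, so the gain is small when f is small. The date of the last prior dose is needed, and SAP Section 15 says last dose dates in the 12-week period cannot be taken as known without assumptions. That date should be established for re-entrants.

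**Protocol.** The sponsor should reconcile exclusion 9, including its randomization anchor, with inclusion 4 and with the Screening-referenced QTcF change in 6.1.4. It should also reconcile the Day 1 pre-dose ECG in Appendix 3 footnote 14 and SAP 5.3.1.5 with its absence from the schedule table and Visit 2 list. The aim is to state which values are off-drug references. How this is done, including any effect on time off drug, is for the sponsor's clinical team.

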Cohort 4 (adults) and Cohort 6 (11-17 years) will initiate concurrently at 200mg BID (200 mg BID has been previously evaluated in adults in study SPR001-201). Upon completion of the 4-week dosing on 4 sentinel participants from Cohorts 4 and 6 combined, the DMC will assess safety data and provide recommendations on continued dosing. If the DMC assesses it to be safe to proceed to a higher dose, Cohort 5 (adults) may be initiated at 300mg or 400mg BID and Cohort 7 (2-10 years) may be initiated at 200mg BID. Following the completion of the 4-week dosing periods for Cohorts 5 and 7, the DMC will review safety data from 4 sentinel participants and offer recommendations on whether to proceed to Cohort 8 (11-17 years) and at what dose (300mg or 400mg BID). Following completion of Cohort 8, the DMC will review the safety data from 4 sentinel participants and provide a recommendation on whether to proceed with Cohort 9 and at what dose (300mg or 400mg BID) ([Table 1](#)).

All cohorts including doses above 200 mg BID will be adaptive, so that the determination to initiate a cohort, and at what dose, may be determined by the Sponsor, within the guidelines of the protocol, based on recommendations by an independent Data Monitoring Committee (DMC) and emerging safety and exposure data. Individual and study stopping criteria will further ensure safety of the participants.

Please see [Section 3](#) for details on Study Design and [Section 6](#) for details on stopping criteria.

Study Conduct: There are 7 scheduled visits over approximately 18 weeks for Cohorts 1 to 3; and 5 scheduled visits over approximately 10 weeks for Cohorts 4 to 9. Visits are detailed in the Schedule of Activities. All visits should be performed on site, but alternative arrangements may be used if an on-site visit is not feasible. Adverse events and concomitant medications will be collected at each visit.

Any participant enrolled under protocol amendment 3 may be re-consented to protocol amendment 4 and receive the 12-week treatment course; however, because they will have already contributed PK data, they will not be required to have blood draws for tildacerfont concentration on Days 1 and 14 between 0.5 to- 1.5 hours and between 3 to 5 hours post dosing. Additionally, any participant enrolled under amendment 4 (or any other tildacerfont study) may be re-consented and enrolled under protocol amendment 5.

Please see [Section 3](#) and [Section 10.2](#) for details on Study Conduct.

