1.3. Risk/Benefit Assessment

Tildacerfont has been generally well tolerated at effective doses and has demonstrated the ability to reduce ACTH and downstream adrenal androgen production in adult patients with CAH and elevated adrenal androgen levels in Phase 2a studies. The most frequently reported non-procedural associated adverse events (AEs) were headache and diarrhea. No drug-related SAEs have been reported in completed clinical studies to date.

Potential clinically significant risks identified in the pre-clinical program include histopathological changes in the thyroid gland and male reproductive tract, developmental toxicity and mild, possibly treatment-related trends in increased Fridericia-corrected QT interval (QTcF) duration. However, no corresponding functional decline in thyroid or male reproductive biochemical assessments has been observed in human studies completed to date, nor have any cardiovascular safety concerns been noted with either vital signs or electrocardiogram (ECG) monitoring. Developmental toxicity has not been evaluated in human clinical trials.

Hepatic effects were also noted in the pre-clinical program, and reversible liver enzyme elevations have been observed in clinical studies.

Additional details of known and potential risks of tildacerfont are provided in the IB. Study SPR001-205 has incorporated multiple design elements to mitigate these potential risks including extensive laboratory assessments ([Section 7.1.5](#)), an independent Hepatic Adjudication Committee to assess potential liver issues, ECG monitoring ([Section 7.1.4](#)), contraception requirements ([Section 4.2.3](#)), and stopping criteria ([Section 6.1](#)).

As tildacerfont is metabolized by CYP3A4, drug-drug interaction risk necessitates the prohibition of concomitant use of known moderate to strong inducers or inhibitors of CYP3A4. Moreover, as tildacerfont is a moderate inhibitor of CYP3A4, drugs that are sensitive substrates or narrow-therapeutic-range substrates of CYP3A4 and/or breast cancer resistance protein (BCRP) must be avoided; for sensitive substrates or narrow-therapeutic-range substrates of BCRP in the absence of CYP3A4, cautionary use is advised with separation of at least 10 hours from tildacerfont and ongoing assessment for loss of efficacy.

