Once safety data are available for Cohort 5 and 7 sentinels, the DMC will convene and make a recommendation regarding initiation of pediatric cohorts at doses >200 mg BID. The Sponsor will then decide whether to initiate Cohort 8 at a dose up to 400mg BID. Subsequently, the DMC may review data from 4 sentinels from Cohort 8 and make a recommendation regarding further dose increase in the younger age group. Sponsor may then decide whether to initiate Cohort 9 at a dose up to 400mg BID.

A sparse serial blood sampling approach for PK will also be used in Cohorts 4 to 9 on Day 1 (Visit 2) and Week 2/Day 14 (Visit 3). Blood samples for tildacerfont concentration should be obtained pre-dose and between 0.5 - 1.5 hours and 3 - 5 hours post dosing. At these visits, participants will dose in clinic with a meal at 8 am (± 1 hour).

All participants in Cohorts 4-9 will receive open-label tildacerfont for the 4-week treatment period, after which they may be offered optional continued treatment if the clinical Investigator believes it is in the participant's best interest. Once enrolled in the extension period, participants may adjust tildacerfont dose up to the highest dose recommended by the DMC per age group at the Investigator's discretion.

Table 1. Study Cohorts

Cohort	Age	Corresponding Adult Dose	Subject Numbers	Treatment Duration
1	11- to 17-years	50 mg QD	5	12 Weeks
1a ^a	11- to 17-years	To be determined based on DMC recommendation (50 or 100 mg QD)	5	
2	11- to 17-years	200 mg QD	5	
3	2- to 10-years	50 mg QD, 100 mg QD, OR 200 mg QD	10	
4	≥ 18 -years	200 mg BID	5	4 weeks
5	≥ 18 -years	300 and/or 400 mg BID	5+5 ^c	
6	11- to 17-years	200 mg BID	5	
8 ^b	11- to 17-years	300 and/or 400 mg BID	5+5 ^c	
7	2- to 10-years	200 mg BID	5	
9 ^b	2- to 10-years	300 and/or 400 mg BID	5+5 ^c	
			Up to 70 subjects total	

Abbreviations: BID=twice daily; DMC=Data Monitoring Committee; QD=once daily.

^a Cohort 1a is an optional interim dose cohort that may be enrolled only if needed per DMC recommendation and Sponsor decision, in the event of a safety concern in participants in Cohort 1.

^b Cohort 8 and 9 are adaptive cohorts that may be enrolled based on emerging safety data and per DMC and Sponsor recommendation/approval.

^c+5 allows for the option of dosing 300mg before or after 400 mg Cohort is initiated if indicated by the DMC

A schema of the study design is presented in [Figure 1](#) for Cohorts 1, 1a, 2, and 3; and in [Figure 2](#) for Cohorts 4, 5, 6, 7, 8, and 9.

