3.1.3. Extension Period

Participants who complete the 12- or 4-week treatment period, depending on cohort, may be eligible to continue dosing to complete 2 years on treatment in an extension study. Participants will sign a separate informed consent form at Week 12 or Week 4. Pending DMC review, participants in Cohorts 1 and 1a (if indicated) will receive the adult equivalent dose of 200 mg QD during the extension (i.e., Cohort 1 participants will immediately switch to 200 mg equivalent if the DMC has already recommended this dose for Cohort 2, or participants may enter the extension period on 50 mg equivalent and increase to 200 mg equivalent after such a recommendation is made). If a Cohort 1-3 participant is to dose escalate to the 200 mg equivalent, they may do so at the next scheduled visit or come to the clinic for an unscheduled visit and pick up their new supply of study drug. Participants will receive a follow-up phone call 2 weeks after dose escalation to check for AEs.

Further tildacerfont dose adjustments may occur during the extension on a case-by-case basis at the discretion of the Investigator with Sponsor approval. Any extension participant may receive the highest dose recommended by the DMC for their age group. Dose changes (increase or decrease) may occur at a scheduled visit, an unscheduled visit, or via a phone visit, but any dose escalation > 200mg QD will be followed by safety labs (link to list) within 2-4 weeks of the change. Once all participants are in the extension period, safety- data will be reviewed every 6 months by the DMC. Weight-based dose adjustments may be made at any extension visit, with no follow-up labs required.

For Cohorts 1-3, the first visit of the extension will be Week 12. For Cohorts 4-9, Week 4 will be the first extension visit, followed by extension clinic visits at Weeks 8 and 12 (\pm 2 weeks). Starting at Week 12, all participants will attend clinic visits every 12 weeks (\pm 2 weeks).

Approximately a 12-week supply of study drug, as appropriate, will be dispensed at each visit. Approximately 30 days after the last dose of study drug, participants will have a final follow-up visit conducted by telephone. Concomitant medications and AEs will be reviewed. If any ongoing safety issues are identified, the participant may be asked to visit the clinic for additional tests, labs, or assessments.

The extension study visits will include the following:

- Review concomitant medications for any changes

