5.2.4. Preparation and Administration

Participants will be taking between 1 and 6 tablets daily, depending on the dose and Cohort assignment. Participants can either swallow the tablet[s] whole or crush the tablet[s] and sprinkle on soft foods.

Cohorts 1 to 3 will receive doses QD. The dose will be taken with the evening meal. The first 2 weeks in Cohorts 1, 1a, and 2 will require dosing with a morning meal.

Cohorts 4-9 will receive BID dosing. Each dose should be taken with the morning and evening meal.

If necessary, the study drug may be taken up to 30 minutes after completing the meal(s) at home. If a participant has not consumed study drug within 30 minutes following the meal(s), the participant should consume study drug with a snack. Study drug will be dispensed at Day 1 for the duration of the study.

The Day 1 and Day 14 morning doses of tildacerfont will be administered in the clinic for Cohorts 1, 2, 4, 5, 6, 7, 8, and 9 (and 1a, if indicated) and Day 1 only for Cohort 3. Any remaining study drug will be returned for accountability at Visit 6 (Week 12) for Cohorts 1 to 3 and Visit 4 (Week 4) for Cohorts 4 to 9, any early termination (ET) Visits, and during extension visits. The Investigator is responsible for ensuring that dosing is administered in compliance with the protocol.

Preparation and administration instructions are included in the Pharmacy Manual.

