5.3.2. Prohibited Concomitant Medications

- Use of other investigational drugs and devices are prohibited during the study.
- Rosiglitazone, testosterone, growth hormone, or any other medication or supplement that could impact participant safety or confound interpretation of study results are prohibited.

- Moderate to strong inhibitors and/or inducers of cytochrome P450 3A4 (CYP3A4); this includes consumption of grapefruit, grapefruit juice, or any foods that are known to be strong CYP3A4 inhibitors from 1 day before the first dose of study drug until after the final dose.
- Sensitive substrates or narrow-therapeutic-range substrates of CYP3A4 (e.g., dexamethasone and oxycodone)
Note: This does NOT apply to hormonal contraception containing ≤20 mcg ethinyl estradiol.
- Sensitive substrates or narrow-therapeutic-range substrates of BCRP (except those that can be administered QD in the morning, separated by approximately 10 hours from evening administration of study drug)

[Appendix 5](#) provides a non-exhaustive list of medications, including many commonly used medications, which are prohibited because of their potential for metabolic interactions with tildacerfont. It is critical that each participant's concomitant medications are carefully compared to the list in [Appendix 5](#).

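### The BCRP-substrate exception counts 10 hours from the evening dose only, so under twice-daily dosing it admits a substrate taken with the morning tildacerfont dose

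*Protocol*

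**What the plan says.** Protocol Section 4.1.2, criterion 10d, excludes users of sensitive or narrow-therapeutic-range BCRP substrates "except those that can be administered QD in the morning, separated by approximately 10 hours from evening administration of study drug". The synopsis repeats the criterion. Section 5.3.2 carries it into treatment, again exempting a once-daily morning drug "separated by approximately 10 hours from evening administration of study drug". None of the three texts mentions a morning tildacerfont dose or limits the exception to a dosing schedule.

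Section 1.3 is worded differently. Its general rule is that "drugs that are sensitive substrates or narrow-therapeutic-range substrates of CYP3A4 and/or breast cancer resistance protein (BCRP) must be avoided". For BCRP substrates that are not also CYP3A4 substrates it adds that "cautionary use is advised with separation of at least 10 hours from tildacerfont", with continued checking for loss of efficacy. The separation is from tildacerfont, not from one named dose.

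On schedule, Section 5.2.4 says "Cohorts 4-9 will receive BID dosing. Each dose should be taken with the morning and evening meal". The synopsis states that "Cohort 4 (adults) and Cohort 6 (11-17 years) will initiate concurrently at 200mg BID". In Table 1 of Section 3.1, "Cohort 8 and 9 are adaptive cohorts that may be enrolled based on emerging safety data". Under Section 3.1.3, "Any extension participant may receive the highest dose recommended by the DMC for their age group", so participants from the QD cohorts may also move to BID dosing. The SAP adds no BCRP timing rule.

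**The concern.** The exception makes sense when the only daily dose is in the evening: a morning substrate is then well away from tildacerfont. Once a morning dose is added, the same words point the other way. They steer the substrate to the morning, which is when the second dose is taken, and they count the distance only from the dose that is far away.

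A site applying 10d or Section 5.3.2 literally could therefore enroll or keep a BID participant who takes a BCRP substrate together with tildacerfont. Section 1.3 advises against that. At stake is an eligibility and concomitant-medication rule that disagrees with the protocol's own risk assessment. No endpoint, analysis or sample-size figure depends on it.

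**Working it through.** The plan gives no figure to reproduce. The check is clock arithmetic.

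**Inputs.** Morning and evening dosing for Cohorts 4-9 (Section 5.2.4). In-clinic morning dose at about 8 AM on Day 1 and Week 2 (Section 3.1). About 10 hours from the evening dose (10d, synopsis, Section 5.3.2). At least 10 hours from tildacerfont (Section 1.3). The clock time of the evening dose is not given. I let the daytime gap from morning to evening dose be g hours, and take g = 10 to 14 as a plausible range (assumed).

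**1. What the exception permits on BID.** Put the morning dose at time 0, the evening dose at g, and the substrate at s (negative means before the morning dose).
- Distance to the next evening dose: g − s ≥ 10, so s ≤ g − 10.
- Distance from the previous evening dose: 24 − g + s ≥ 10, so s ≥ g − 14.

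| g (assumed) | Permitted s, relative to the morning dose |
|---|---|
| 10 h | −4 h to 0 h |
| 12 h | −2 h to +2 h |
| 14 h | 0 h to +4 h |

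Every row includes s = 0, and no permitted time is more than 4 hours from the morning dose. For example, with doses at 8 AM and 6 PM (g = 10), a substrate at 8 AM is 24 − 10 = 14 hours after the last evening dose and 10 hours before the next. It meets the exception at 0 hours from the morning dose.

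**2. Whether Section 1.3 can be met on BID.** The farthest point from the nearest dose is max(g, 24 − g)/2.
- Gaps of 12 and 12 h: 12/2 = 6 h.
- Gaps of 10 and 14 h: 14/2 = 7 h.
- Gaps of 8 and 16 h: 16/2 = 8 h.

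To reach 10 hours, one gap must be at least 2 × 10 = 20 h, which leaves the two doses at most 4 h apart. Morning and evening meals do not allow that. With one dose a day the farthest point is 24/2 = 12 h, so 10 hours is attainable on QD.

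**3. Places on a BID schedule (Table 1).** Cohorts 4 and 6, which open first: 5 + 5 = 10. All of Cohorts 4-9, if every optional group is filled: 5 + 10 + 5 + 5 + 10 + 10 = 45. Extension participants moved to BID would be additional. These are enrollment places, not users of BCRP substrates.

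**The case against.** The best answer is that the protocol, read as a whole, already reaches the safe result. Section 1.3 starts from avoidance and allows use only at a separation that BID dosing cannot provide, so avoidance applies. That is a fair reading, and it makes this a harmonization error rather than a missing principle. It does not cure the operational texts. Sites screen against 10d and manage medications under Section 5.3.2, and both state an express exception that a BID participant can satisfy.

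The safeguards also count. Appendix 5 prohibits its listed drugs outright, so the exception matters only for unlisted substrates, and it asks that drugs of concern go to the Medical Monitor. Section 5.3 asks participants to report new medications at once and directs questions to the Medical Monitor. Criterion 10a is a general safety clause. These lower the risk. They do not tell a site that a specific exception is unavailable, and the Appendix 5 list is described as non-exhaustive. Criterion 10 and Section 5.3 also refer sites to Appendix 3, which is a schedule of activities. Appendix 5 remarks that most children will not be taking the listed drugs. That suggests low use, though it does not speak for the up to 15 adults in Cohorts 4 and 5.

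A reader might infer three stronger points that the documents do not support.
- **Dose-related danger.** BID cohorts take higher daily doses than the QD cohorts. But the documents give neither the size of the BCRP interaction nor any dependence on dose. The separation wording in Section 1.3 is advisory, and the only consequence it names is loss of efficacy.
- **Ten to 45 people affected.** That range counts places. Only Cohorts 4 and 6 open without a further DMC step, and no number of users is stated.
- **The same fault in Cohorts 1-3.** In the first two weeks of Cohorts 1, 1a and 2 there is no evening dose, so the exception is better read as not met. In Cohort 3 the supervised Day 1 morning dose is one occasion. Section 3.1.2.3 is unclear on whether a second one occurs at Week 2, so no instruction should be built on it.

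**Conclusion.** The point holds as a wrong stated rule, not as missing detail. As written, 10d, the synopsis and Section 5.3.2 permit a BCRP substrate at or near the morning tildacerfont dose under BID dosing. The 10-hour separation in Section 1.3 cannot be met on that schedule, where the best attainable is about 6 to 8 hours.

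Confidence in the textual conflict is high. That a substrate taken with the morning dose qualifies rests on an assumed daytime gap of 10 to 14 hours. That 10 hours is unattainable rests only on the two doses being more than 4 hours apart. The practical effect is probably small and cannot be sized from the documents. The change is worth making because it concerns safety wording and is cheap.

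**What to change.** In criterion 10d, the synopsis and Section 5.3.2, add that the exception applies only while tildacerfont is taken once daily in the evening. State that during BID dosing, including in the extension, sensitive or narrow-therapeutic-range BCRP substrates are prohibited unless the Medical Monitor approves a justified plan for that participant. Put the same BID statement in Section 1.3, so that its 10-hour advice is not read as available on a schedule where it cannot be met.

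The cost is wording in four places. The downside is that a few BID candidates may need a substitute drug or Medical Monitor approval, or may be excluded.
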